### **Management of Psychosomatic Disease According to Yoga**

As discussed above, ādhi in manomaya koṣa is the source for psychosomatic diseases, which manifest as imbalance tridoṣa at the physiological level. Hence, the treatment approach for psychosomatic medication should include such interventions that can correct the imbalance both at the mind level as well as body level. Following module based on ancient methods of Yoga is thus proposed, to control and prevent the psychosomatic disorders.

#### Key questions expected to be answered by this study:

- a) What are the effects of yoga on biochemical and molecular markers of stress leading to changes in DNA damage response
- b) Is there any change in the DNA repair capacity of yoga-practicing subjects as compared to matched controls?
- c) What will be the mechanism by which yoga modulates DNA damage response and repair.

## **Definition of the problem**

Evaluate the molecular impact of yoga on DNA damage response and repair on security guards of Chandigarh Police

## **Objectives**

1. Analysis of molecular markers related to DNA damage response and repair before and after the practice of yoga on Chandigarh Police
2. To examine the molecular mechanism by which yoga may modulate DNA damage response and repair.

## **Review and status of Research and Development in the subject:**

Chronic stress and anxiety leading to various lifestyle disorders have become a common problem in today's world and the current health care industry is unable to resolve this vicious cycle. This has led to development of alternative approaches to wellness that can improve the overall health of individuals and can even prevent various life-threatening diseases. Various studies have suggested that yoga can be beneficial for the treatment of many psychological disorders like anxiety; depression etc. and can prevent cognitive impairment of the aging individuals. Numerous studies have shown yoga as a holistic approach for the well being of an individual that affects the overall physiology. However, these effects have not been studied at the molecular level.

Policemen need to be alert for a long duration of time and hence remain in chronic stress. Many of them suffer from depression, stress and anxiety and have undergone the extreme step of committing suicide. Quite understandably, this distress can have a huge impact on their professional and personal life. Various studies have shown that chronic mental stress can further accentuate stress at the cellular and molecular level. This long-term stress and anxiety, thus, is a prelude to various chronic diseases like diabetes, hypertension and even life-threatening diseases like cancer (Mariotti et al., 2015). Cancer is a life-threatening disease due to rapid uncontrolled cell growth and most of the cancers show altered DNA damage response and repair capacity.

## **International status:**

Yoga-based lifestyle intervention (YBLI) is being recognized as an adjunct to modern medicine in order to treat many medical conditions including stress and lifestyle-based disorders, chronic inflammatory disorders and metabolic syndromes (Yadav et al., 2012). Various clinical trials across the globe have shown the beneficial effects of yoga on cancer patients in terms of overall improvement in the quality of life and mood states (Rao et al., 2017). However, these trials are heterogeneous as various types of asanas were performed. Carlson et al. showed that telomeric length was maintained in the intervention group while it was decreased in the control participants, though no

associations were found between changes in telomeric length and mood or stress scores (Carlson et al., 2015). Lengacher et al. studied the effect of yoga intervention on breast cancer patients and found a steady increase in telomerase activity while the length of telomeres did not change (Lengacher et al., 2014). A similar clinical trial by Kiecolt et al. observed a reduction in inflammation and fatigue in breast cancer patients (Kiecolt- Glaser, 2014). Chandwani et al. integrated yoga regime in stage I-III breast cancer patients, and stage 0-III, breast cancer patients undergoing radiotherapy (Chandwani et al., 2014). They checked for the changes in fatigue, depression, sleep quality, and salivary cortisol. Interestingly, they found a significant improvement in the quality of life along with physiological changes associated with radiotherapy. Systematic evaluation of the effect of yoga as a complementary intervention in cancer therapy has proposed that yoga is associated with positive effects on psychological functioning (Smith & Pukall, 2009). A report demonstrated the potential effect of yoga intervention on telomeric length of breast cancer survivors (Carlson et al., 2015). This study thus supports association between genetic alterations, cancer initiation and survival, leading to an increase in data that shows an important role of disease-regulating processes and outcomes (Epel et al., 2009). Though Lotzke et al. did not find any significant difference between the intervention and control groups when the study was done in stage I-III breast cancer patients (Lotzke et al., 2016), a detailed molecular study has demonstrated that stress can evade apoptosis and can promote prostate carcinogenesis in mice in an epinephrine-dependent manner (Hassan et al., 2013).

#### **National status:**

Yoga may help in managing distress and modulate circadian rhythms in early breast cancer patients undergoing neoadjuvant radiotherapy (Vadiraja et al., 2009). However, various studies show heterogeneity in benefits of yoga depending on the extent of intervention, practice, duration and indications (Rao et al., 2017). A recent study demonstrated that YBLI protects sperms from oxidative stress, reduces sperm DNA damage that in turn leads to an improvement in sperm motility and count (Dhawan et al, 2018). A similar study showed a significant improvement in the markers of cellular aging in 96 healthy individuals after YBLI (Tolahunase et al., 2017). Recent studies have

shown that increase in the incidence of childhood cancers can be attributed to oxidative stress leading to DNA damage in sperms. YBLI led to a significant improvement in oxidative DNA damage markers in 131 fathers of children with Retinoblastoma (Dada et al., 2016).

### **Novelty of the study:**

In this study, we are investigating the detailed molecular mechanisms by which yoga can modulate DNA damage response and repair. Although multiple studies have examined the effect of yoga on DNA damage repair, a detailed mechanism by which yoga improves high-fidelity DNA double strand break repair is lacking.

Human DNA is exposed to both endogenous and exogenous sources of DNA damage. Endogenous sources of DNA damage mainly include oxidative free radicals while exogenous sources like UV radiation, X-rays, chemicals etc are the sources of DNA strand breaks and major sources of cancer. Most of the studies have focused on effects of yoga on oxidative stress by using 8-OHdG as a marker. Few studies have used comet assays, expression of PARP1 and telomerase activity to evaluate DNA strand damage and repair. These preliminary studies provide for the platform to further evaluate the effect of yoga on DNA damage response and repair at the molecular level. In this proposed study, using various techniques, we will examine the detailed molecular mechanism by which yoga may tweak DNA damage response and repair mediated tumorigenesis using both in vitro (cell lines) and in vivo (human subjects)models.

### **Importance of the proposed project in the context of current status**

We already have evidence of association of psychological stress with DNA damage. A lot of studies also suggest that Yoga has a positive effect on stress and DNA damage. However, the mechanism of how yoga affects the DNA damage response and DNA repair pathways is not known. To the best of our knowledge, no study in literature has tried to assess the effect of yoga on DDR and DNA repair pathways at the molecular level. Therefore, in the present study we propose to investigate the role of yoga in modulating DNA damage response and repair which will further help in understanding if yoga can prevent life-threatening diseases like cancer. This study can further be extended to evaluate if yoga can potentiate the therapeutic efficacy of anti-cancer drugs.

## Work plan:

[figure not shown]
### Methodology

Recruitment of individuals: Department of Police, Chandigarh has agreed to help us on this aspect. Policemen working for Chandigarh Police will be chosen based on the inclusion and exclusion criteria.

Subjects: Those security guards (age: >20 and <60) who are willing to consent to participate in this study will be screened for moderate and higher stress on Cohen's PSS, according to inclusion criteria and randomly divided between Intervention (Yoga Group) and Control Group.

Sample Size: The sample size of 206 was calculated for 99% confidence level (reliability coefficient = 2.58), at the alpha level of 0.05, a power of 0.95, and a relative precision of 0.2, derived from a pilot study done on breast cancer patients and yoga practitioners (Ram et al, 2013). Assuming a 10% drop out rate, a total of 229 subjects will be recruited.

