### **Design of the study**

In a randomized control trial (RCT), participants are allocated randomly between intervention and control groups to compare the treatments, which enables statistical control over the influences imparted by the aforementioned treatments. In the present study, the policemen who satisfy our eligibility criteria and willing to consent to participate in our study will be enrolled, grouped randomly in intervention and control groups, and assessed for the dependent variables of the study before and after the Integrated Yoga intervention period.

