### **Variables**

- Socio-demographic details – age, diet, alcohol consumption, etc.
- Evaluation of stress level on Cohen's Perceived Stress Scale (pre and post intervention) (Cohen, Kamarck & Mermelstein, 1983)
- Evaluation of stress level using vital parameters: Blood pressure and resting heart rate of participants will be recorded pre and post intervention.

- Evaluation of stress level using molecular parameters: (pre and post intervention) 10 ml of blood will be withdrawn from the subjects by trained phlebotomists, and coded. WBCs and plasma will be separated using standard protocols and stored at -80°C. Plasma will be utilized to assess the levels of cortisol.
- Assessment of chromosomal translocations: (pre and post intervention) Genomic DNA will be extracted from WBCs isolated, and tested for chromosomal translocations using PCR assay. Isolated genomic DNA will be subjected to nested PCR using primers specifically designed to check for t(14;18) and t(11;14) translocations.
- Assessment of DDR and DNA repair:
- *Immunofluorescence*: Isolated PBMCs will be subjected to DDR analysis by immunofluorescence. For this, these cells will be fixed and stained with various DDR markers like γH2AX, 53BP1, pATM.
- *Gene expression analysis*: Total RNA will be isolated from these cells; cDNA will be synthesized and the expression of following DDR and DNA repair genes will be performed using real-time PCR: RAD51, MRE11, RAD50, NBS1, KU70, LIGASE IV, PARP1
- *Comet assay*: Cells will be used to perform both the neutral as well as alkaline comet assay to assess for the number of single- and double-strand breaks.
- Telomeric length: Relative telomere length (TL) using quantitative polymerase chain reaction (qPCR) will be performed on genomic DNA isolated from control and group blood samples and will be compared.

Time Line for experiments:

S.No.	Experiments	Time point
1.	Cortisol levels	0 day
2.	DDR: Immunofluorescence for γH2AX, 53BP1, and ATM.  Gene expression analysis for KU70, LIGASE IV, RAD51,	0 day

	PARP1, MRE11, RAD50, NBS1	
3.	Nested PCR for Chromosomal Translocations	0 day
4.	DNA repair: Comet assay	0 day
5.	Cortisol levels	3 months
6.	DDR: Immunofluorescence for $\gamma$ H2AX, 53BP1, and ATM.  Gene expression analysis for KU70, LIGASE IV, RAD51,  PARP1, MRE11, RAD50, NBS1	3 months
7.	Nested PCR for Chromosomal Translocations	3 months
8.	DNA repair: Comet assay	3 months

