Date: February 29, 2020

NCT number: Not

Available

Official Project Title

Investigating the Role of Yoga in Alleviating
Chromosomal Translocations in Security Guards
of Chandigarh Police Who Are Responsible for
the Safety of VIPs

Statistical Analysis Plan (SAP)

1. Introduction

This Statistical Analysis Plan (SAP) outlines the planned analyses for the study titled “Investigating the Role of Yoga in Alleviating Chromosomal Translocations in Security Guards of Chandigarh Police Who Are Responsible for the Safety of VIPs”. It defines the methods for analyzing study endpoints, including descriptive, inferential, and correlation analyses.

2. Objectives and Endpoints

1. Analysis of molecular markers related to DNA damage response and repair before and after the practice of yoga on Chandigarh Police.
2. To examine the molecular mechanism by which yoga may modulate DNA damage response and repair.

3. Analysis Populations

- **Full Analysis Set (FAS):** All participants meeting eligibility criteria and providing baseline and outcome data.
- **Per-Protocol Set (PPS):** Subset of participants completing the study without major protocol deviations.

4. General Statistical Considerations

- All analyses will be conducted using **GraphPad Prism v8.0.2** and **JASP v0.19.3**.
- Two-sided significance level of $\alpha = 0.05$ will be applied.

- Adjusted p-values from post hoc tests will also use the **0.05 threshold** for significance.
- Continuous variables will be summarized with **mean \pm SD** (if normally distributed) or **median with interquartile range** (if non-normal).
- Categorical variables will be summarized as **frequencies and percentages**.

5. Assessment of Assumptions

- **Normality:** Assessed using the **Shapiro-Wilk test**.
- **Homogeneity of variance (ANOVA assumption):** Checked using **Levene's test**.

6. Statistical Methods

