6.3 Correlation Analyses

- **Normally distributed data:** Pearson's correlation coefficient.
- **Non-normal data:** Spearman's rank correlation coefficient.

7. Handling of Missing Data

- Data will be analyzed as observed (complete case analysis).
- No imputation will be performed unless otherwise specified in the protocol.

8. Interim and Sensitivity Analyses

- No interim analyses are planned.
- Sensitivity analyses may be conducted to confirm robustness of results (e.g., excluding participants with protocol deviations).

9. Reporting

- Results will be presented in accordance with **CONSORT/CONSORT-Extension guidelines**.
- Statistical outputs will include effect sizes, 95% confidence intervals, and exact p-values.

Principal Investigator

[name]

Additional Professor

Department of Experimental Medicine and Biotechnology

PGIMER, Chandigarh

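### The sample size of 206 is stated at two error levels (99% confidence with z = 2.58, and alpha 0.05), and its 95% power is tied to no endpoint or difference

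*Protocol*

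**What the plan says.** The Sample Size paragraph of the protocol's Methodology section gives 206 for "99% confidence level (reliability coefficient = 2.58), at the alpha level of 0.05, a power of 0.95, and a relative precision of 0.2". It describes the figure as "derived from a pilot study done on breast cancer patients and yoga practitioners", but reports no value from that pilot. A 10% dropout allowance then takes the total to 229.

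The same section says guards will be "randomly divided between Intervention (Yoga Group) and Control Group". The Design of the study section explains a randomised trial as one in which "participants are allocated randomly between intervention and control groups to compare the treatments" and then applies that design to this study. The first objective is worded differently: "Analysis of molecular markers related to DNA damage response and repair before and after the practice of yoga on Chandigarh Police".

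SAP section 4 says "Two-sided significance level of $\alpha = 0.05$ will be applied", and SAP section 9 says "Statistical outputs will include effect sizes, 95% confidence intervals, and exact p-values". The SAP has no sample-size section and names no primary endpoint.

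**The concern.** Three things in the sample-size sentence do not fit together.

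- **Two error levels for one N.** A coefficient of 2.58 belongs to a two-sided alpha of about 0.01; two-sided alpha 0.05 has 1.96. The coefficient is printed, so the 99% is not a slip in the percentage alone. Nothing in the SAP uses 99%.
- **Two kinds of calculation.** Relative precision is an input to an estimation calculation, and the standard precision formula contains no power. A power of 0.95 belongs to a test against a stated difference. The text does not say which calculation produced 206, or that 206 satisfies both.
- **A power with no target.** The sentence gives no endpoint, SD, proportion or difference. The Variables section lists many markers, from cortisol to comet assays to telomere length, and singles out none.

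A reader therefore cannot tell what yoga-versus-control difference 206 guards can detect, or at which error level. A null between-arm result would be read against a 95% power figure that the stated inputs do not support.

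**Working it through.** **Inputs from the documents.** N = 206; z = 2.58; alpha = 0.05; power = 0.95; relative precision e = 0.2; dropout 10%; two randomised arms. **Not given in readable text:** endpoint, SD, coefficient of variation (CV), proportion, effect size, allocation ratio.

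**1. The plan's own figures.** Dropout: 206 / 0.9 = 228.9, so 229. This reproduces. The 206 itself cannot be reproduced, because every route needs an input that is not stated:

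- Precision of a mean, n = z² CV² / e². With z = 2.58, 206 requires CV = √(206 × 0.04 / 6.656) = 1.11. With z = 1.96 it requires 1.46.
- Precision of a proportion, n = z² (1 − p) / (p e²). With z = 2.58, 206 requires p = 0.447. With z = 1.96 it requires 0.318.
- Two-arm test, total n = 4 (z_α + z_β)² / d². At two-sided 0.05 and 95% power, d = 0.5 gives 4 × 3.605² / 0.25 = 208. This is close to 206, but d = 0.5 appears nowhere.
- Reading 0.2 as a standardised effect at 95% power does not give 206. A paired test needs 325 (alpha 0.05) or 446 (alpha 0.01); two arms need 1300 or 1782 in total.

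**2. The two error levels.** 2 × (1 − Φ(2.58)) = 0.0099, against the stated 0.05.

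**3. How much the choice of level matters, all else fixed.** No formula is printed, so both lines illustrate sensitivity and do not measure an error in 206.

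| Formula | Ratio of N, z = 2.58 to z = 1.96 | If 206 used 2.58, N at 1.96 | If 206 used 1.96, N at 2.58 |
|---|---|---|---|
| One-sample precision | (2.58 / 1.96)² = 1.73 | 206 / 1.733 = 119 | 206 × 1.733 = 357 |
| Two-arm test, 95% power | (4.225 / 3.605)² = 1.37 | 206 / 1.374 = 150 | 206 × 1.374 = 283 |

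Here 4.225 = 2.58 + 1.645 and 3.605 = 1.96 + 1.645.

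**4. What the fixed N can detect.** Assumptions: continuous endpoint, 1:1 allocation, 206 / 2 = 103 evaluable guards per arm, two-sided t-test (noncentral t).

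| Comparison | Alpha | 95% power | 80% power |
|---|---|---|---|
| Yoga versus control, 103 per arm | 0.05 | 0.505 | 0.392 |
| Yoga versus control, 103 per arm | 0.0099 | 0.59 | 0.48 |
| Before versus after within yoga, 103 pairs | 0.05 | 0.36 | 0.28 |

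The first two rows are in SD units of the endpoint compared, the third in SDs of the within-person change. As a check on the first row, the normal approximation gives 3.605 × √(2 / 103) = 0.502. At a between-arm difference of 0.505, power is 95.0% at alpha 0.05 and 84.5% at alpha 0.0099.

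**The case against.** **The two levels could coexist.** One N can meet a 99% precision target and a separate test at alpha 0.05 with 95% power, for example as the larger of two requirements. Estimation is not confined to one arm either, since a between-arm difference can also be estimated to a target precision. Both points stand, so the levels should not be called incompatible. But the text sets out neither calculation and does not say that 206 is the larger of two.

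**The power may refer to a before-after change.** The objectives and the project summary speak of results before and after yoga, SAP section 6.1 allows paired tests, and the sentence about comparing treatments is a general description of randomised trials. This is a real ambiguity, and the fix must cover it. Against it, the guards are randomised to a control arm, and one of the protocol's key questions compares repair capacity with controls. A within-arm change would not answer that question.

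**The inputs may exist elsewhere.** Part of the protocol, including the work-plan figure and the flow chart on sample allocation, cannot be read, and the pilot's values are not reproduced. The statement about missing inputs is therefore limited to readable text. The clash between 2.58 and 0.05 is not affected.

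**The analysis is unaffected.** True: the SAP sets one level. What is at fault is the justification of the sample size.

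**Conclusion.** The point holds in limited form and should be fixed. One N carries two error levels, only one of which the SAP uses, and the 95% power is not supported by the stated inputs for the randomised comparison. The mismatch of levels is certain. The lack of a basis for the power is established for readable text only.

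A reader might infer that 206 is too small, that the trial is underpowered, or that the 95% figure is false. The documents support none of these. Unstated but possible inputs give about 206 on either route (CV of 1.11 at z = 2.58, or d = 0.5 at alpha 0.05), so the figure is unverifiable and not shown to be wrong. The factors of 1.73 and 1.37 depend on formulas inferred here. The detectable differences rest on 1:1 allocation, 103 evaluable guards per arm, a continuous endpoint and a t-test.

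**What to change.** Keep 229 enrolled and amend the sample-size paragraph.

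1. Use one error level, two-sided alpha 0.05, as in the SAP.
2. Remove the 99% and 2.58 figures from the power statement, or label them as a separate precision calculation and give its formula, measure and pilot values.
3. Replace the unqualified power of 0.95 with what the fixed N can detect for one named endpoint. For a continuous endpoint compared between arms, suitable wording is:

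> Assuming 1:1 allocation and 103 evaluable guards per arm, a two-sided t-test at alpha 0.05 has 95% power for a standardised between-arm difference of about 0.51, and 80% power for about 0.39, in [named endpoint], standardised by the SD of [change scores or post-intervention values].

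Present these as detectable differences, not as expected or clinically meaningful ones.

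4. If the intended claim is the change within the yoga arm, state it separately: 103 pairs give about 0.36 SD of change at 95% power and 0.28 at 80%. Say that this is not evidence about yoga versus control.
5. Recompute if allocation is not 1:1, if another test is used, or if the endpoint is binary, as it may be for the "nested PCR using primers specifically designed to check for t(14;18) and t(11;14) translocations".

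Cost: no extra participants and no change to conduct. One endpoint must be chosen from the many listed, which is a design decision and more than wording. The stated sensitivity will also look less favourable than an unqualified 95%.

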### Flow Chart 3: Allocation of Sample Size According to Consort Guidelines

### *Inclusion criteria*

- i. Guards scoring more than 15 points on Cohen's scale. Once these subjects' consent to enroll, each one of them will be coded to maintain anonymity.
- ii. Both males and female guards of age 20 to 60 years.

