### **Project summary:**

Policemen recruited in the Chandigarh police who take care of the safety of VIPs most likely suffer from chronic stress, as they need to be vigilant round the clock. Since chronic stress has been shown to be responsible for multiple molecular changes at both the genomic and epigenomic levels, it can lead to various diseases like hypertension, diabetes and even cancer. Further, it has been shown that deregulation in DNA Damage Response (DDR) and DNA repair pathways is responsible for cancer. Though it is well known that yoga relieves stress and anxiety, literature lacks in studies that focus onto assessing the effect of yoga on DDR and DNA repair pathways at the molecular level. In the present study, we propose to investigate the role of yoga in modulating DDR and repair. For this, personnel of Chandigarh police who need to be extra vigilant could be the ideal cohorts. A sample size of around 230 security guards from Chandigarh police shall be recruited in the study with their consent, upon screening them for mild or severe stress on Cohen's Perceived Stress scale. 10 ml of blood will be withdrawn from the participants followed by separation of serum, plasma and WBCs from these subjects. Biochemical assays to measure the levels of cortisol (stress marker) will be performed and analyzed. This study proposes to analyze DDR markers like  $\gamma$ H2AX, 53BP1, and ATM and the extent of damage in WBCs using comet and DNA repair assays. Post the baseline assessments, they will undergo Yoga intervention for a period of 3 months, and at the end of three months, they will be assessed again on the same parameters. The baseline and post intervention results will be compared for discussion and conclusion. This study will help us to understand the effect of yoga in maintaining genomic integrity and stability at the molecular level and can assist the Department of Chandigarh police in designing strategies to improve the overall well being of policemen.

**Key words:** Yoga exercises, DNA damage response (DDR), DNA double-strand break (DSB), DNA double-strand break repair (DSBR), Cancer

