**Total duration in weeks/months for yoga therapy: 3 months (13 Weeks: 5 days a week)**

### **Time schedule of activities giving milestones**

#### First year:

- A. Recruit policemen and get them to fill a questionnaire in order to identify most stressed individuals.
- B. Obtain blood samples, isolate PBMCs, serum and plasma. Biochemical analysis to test for cortisol levels will be performed.
- C. The subjects will be given yoga training for 3 months along with studying DNA damage response and repair using comet assay, immunofluorescence and real-time PCR.
- D. Follow up of the subjects to ensure compliance for yoga protocol.

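### The Perceived Stress Scale is both the entry filter and a pre/post variable, and the plan does not say which score is 'pre'; a within-arm fall could be regression to the mean

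*Protocol*

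**What the plan says.** **PSS as filter.** Under Methodology, guards who are willing to consent "will be screened for moderate and higher stress on Cohen's PSS". Inclusion criterion i sets the cut: "Guards scoring more than 15 points on Cohen's scale". The first-year milestones describe one questionnaire step, at recruitment: "get them to fill a questionnaire in order to identify most stressed individuals". The next milestone is blood sampling.

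**PSS as outcome.** The Variables section lists "Evaluation of stress level on Cohen's Perceived Stress Scale (pre and post intervention". It does not say which administration supplies the pre-intervention score. The 0-day and 3-month table in the same section, headed "Time Line for experiments", has no PSS row at either time point.

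**Comparison.** Guards are "randomly divided between Intervention (Yoga Group) and Control Group", and under Design of the study they are "grouped randomly in intervention and control groups, and assessed for the dependent variables of the study before and after the Integrated Yoga intervention period". The Project summary, however, describes the analysis without a control group: "The baseline and post intervention results will be compared for discussion and conclusion". Objective 1, in both the protocol and the SAP, is also worded as before versus after yoga. SAP section 6.1 leaves the choice between a paired and an unpaired test open. No between-arm PSS contrast and no baseline-adjusted model is named.

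**The concern.** A score selected for being high carries, on average, upward random error, because guards whose error ran downward at screening were left out. A later score from the same guards will be lower on average even if nothing has changed. If the screening score also serves as the pre-intervention value, that drop is counted as change over the three months.

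Two things are at stake. A before/after PSS improvement in the yoga arm, with its effect size, confidence interval and p-value, could be reported as a benefit when part or all of it comes from the selection. The stress level described for the cohort at baseline would also be too high, in both arms.

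**Working it through.** **Inputs from the documents.** Cut: above 15, modelled as 15.5 and over. Evaluable sample: 206. Two-sided alpha: 0.05. The documents give no PSS figure to reproduce. Their recruitment total does reproduce: 206/0.9 = 228.9, rounded up to 229.

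**Assumptions, not in the documents.** PSS SD 6; mean of unselected guards 15, 18 or 20; correlation r between screening and 3 months of 0.5, 0.7 or 0.85; normal scores; no true change; 1:1 allocation, so 206/2 = 103 per arm.

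**Expected fall.** With c = (15.5 − mean)/SD and λ = φ(c)/(1 − Φ(c)), the mean screening score of those admitted is mean + SD × λ, and the fall to the next score is SD × λ × (1 − r).

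Central case, mean 18 and r = 0.7:
- c = (15.5 − 18)/6 = −0.417 and λ = 0.553.
- Admitted guards average 18 + 6 × 0.553 = 21.32.
- Fall = 3.32 × 0.3 = 1.00 point.

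**Paired test within one arm.** The variance of the screening score after selection is 36 × (1 + cλ − λ²) = 36 × 0.464 = 16.7. The variance of the change is (1 − r)² × 16.7 + 36 × (1 − r²) = 1.50 + 18.36 = 19.86, so its SD is 4.46 and its standard error is 4.46/√103 = 0.44. The expected t is 1.00/0.44, about 2.3, and the test rejects in about 61% of null trials. Simulation of the same case gave 63%.

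| Unselected mean | Mean screening score if admitted | Fall at r = 0.5 / 0.7 / 0.85 | Falsely significant, 103 guards |
|---|---|---|---|
| 15 | 20.11 | 2.56 / 1.53 / 0.77 | 99.7% / 94% / 67% |
| 18 | 21.32 | 1.66 / 1.00 / 0.50 | 85% / 61% / 34% |
| 20 | 22.34 | 1.17 / 0.70 / 0.35 | 55% / 35% / 19% |

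Across this grid, 9% to 36% of admitted guards would score 15 or below on a retest with no change in true stress.

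**Between arms.** Both arms pass the same filter, so both fall equally. Null trials were simulated 4,000 times in each of six settings (means 14 to 20, SD 5 or 6, r 0.6 to 0.85), keeping the screening score as baseline. The mean difference in change between arms was −0.01 to 0.00, and the test was significant in 5.0% to 5.8% of trials.

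**Separate 0-day score.** In the same simulations, with a stable true score and independent errors, replacing the screening score by a new 0-day score brought the within-arm change to about 0 and the false-positive rate to 4.4% to 5.6%. This relies on true stress being stable. Suppose instead that screening and 0-day scores correlate 0.85 and each correlates 0.6 with the 3-month score (mean 18, SD 6). The fall from screening is 3.32 × (1 − 0.6) = 1.33 points. The fall from the 0-day score is still 3.32 × (0.85 − 0.6) = 0.83 points, and a within-arm test is falsely significant in about 36% of trials.

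**The case against.** A reader might infer two stronger things.

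**That the screening score is the baseline.** The documents do not say so. The table is a schedule of laboratory assays; it also omits blood pressure and heart rate, which are to be recorded before and after, and the 3-month PSS, which the Variables section requires. A missing row there does not mean that no measurement is taken. Design of the study mentions assessment after eligibility and allocation, which can be read as a new pre-intervention score. The work-plan figure and the body of the CONSORT flow chart are not available in the text. Reuse of the screening score is therefore a possibility that the wording leaves open.

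**That the trial would produce a false yoga effect on stress.** This is not supported either. There is a randomised control arm, assessed at the same times, and the fall cancels in that comparison. The before/after sentence in the Project summary cannot be pinned to PSS: the summary mentions PSS only as a screen and then lists cortisol and DNA-damage assays. The objectives concern DNA damage response and repair, and PSS is not named as primary.

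It is also fair to say that the size is not established. The mean, SD, correlation and allocation ratio are all assumed, and the range is wide.

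These objections narrow the point but leave it standing. The randomised comparison protects the PSS result only if it is the one used, and neither document commits to it. Cancellation also needs comparable arms. Exclusion criterion iv removes non-compliers from the yoga arm only, which weakens that; it is a separate matter.

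**Conclusion.** The concern holds in a limited form. PSS is both filter and outcome, the pre-intervention score is undefined, and a within-arm paired PSS test is permitted. If the screening score is used as 'pre', the yoga arm would show a fall of about 0.35 to 2.6 points with no yoga effect, falsely significant in about 19% to nearly 100% of trials. These figures rest on SD 6, unselected mean 15 to 20, retest correlation 0.5 to 0.85 and 103 guards per arm.

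The harm is confined to within-arm PSS effects and the reported baseline stress level. The between-arm PSS comparison keeps an error rate near 5%, and nothing here touches the molecular endpoints. This is a cheap improvement and does not invalidate the design.

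**What to change.** 1. **Main change, in the SAP:** name the between-arm comparison of 3-month PSS, adjusted for baseline PSS, as the PSS analysis. State that within-arm PSS change is descriptive and is not evidence of a yoga effect. This remedy works even where a new baseline score leaves some regression to the mean.
2. **In the protocol:** use the screening PSS for eligibility only. Repeat PSS at the 0-day visit, before randomisation, and define that score as the baseline and the covariate. Add PSS at 0 day and 3 months to the schedule.
3. **Retention:** analyse guards whatever their 0-day score. Applying the cut again would bring the same selection back.

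The cost is one short questionnaire at a visit that already takes place, two rows in the schedule, and probably a smaller reported before/after fall. N does not change.
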